## 2. Additional Analyses

The additional analyses will be performed for the Full-analysis set.

The following time-to-event endpoint will be analysed by pairwise log-rank tests comparing each active K-321 0.4% treatment regimen to placebo. Kaplan-Meier estimates and plots will also be presented up to Week 52. Patients who complete follow-up or discontinue the study without achieving the specified endpoint will be censored [REDACTED]

- Time to Intervention of Rescue Therapy\*

\*Patient is considered having received rescue therapy if the patient [REDACTED]

The following endpoints based on continuous measures will be analysed by pairwise Wilcoxon rank sum tests comparing each active K-321 0.4% treatment. For [REDACTED] Central corneal Endothelial Cell Density (ECD) assessments, the [REDACTED] data handling methods will be the same as primary analysis, or the Central corneal ECD assessments that could not be performed due to oedema. Otherwise, the [REDACTED] data will be [REDACTED]

[REDACTED]. Patients who receive a rescue keratoplasty will be [REDACTED] or [REDACTED] by [REDACTED], [REDACTED] or [REDACTED], respectively.)

For assessments other parameters, the [REDACTED] data will be [REDACTED]. Additionally, the mean values and standard deviation (SD) by visit will be graphically displayed.

- Central corneal ECD of study eye performed by specular microscopy at [REDACTED]
- Central corneal thickness change from [REDACTED] to [REDACTED].
- BCVA (letters) by ETDRS change from [REDACTED] to [REDACTED]

The following endpoint based on the number and percentage of patients achieving the endpoint will be analysed by Pearson chi-square test comparing each active K-321 0.4% treatment regimen to placebo. The 95% CI for the difference in percentage of patients achieving the endpoint will also be presented. Should the number of responders be less than 5 in either group, Fisher's exact test will be used instead. If Fisher's exact test is used, the unconditional confidence interval for the difference in response rates will be provided. The missing data will be [REDACTED]. Patients who receive a rescue keratoplasty will be [REDACTED]. Additionally, the number and percentages of subjects achieving endpoint by visit will be graphically displayed

- Number and percentage of patients who achieve no corneal oedema

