### **3. Appendix 1 – TLF shells**

**Table 14.2.1.42**  
Time to Achieve Intervention of Rescue Therapy  
(Full Analysis Set)

|   | K-321 QID
(N=XXX) | K-321 BID
(N=XXX) | Placebo
(N=XXX) |
|---|----------------------|----------------------|--------------------|
| Patients with Intervention of Rescue Therapy, n (%)           | XX (XX.X)            | XX (XX.X)            | XX (XX.X)          |
| Time to Archive Intervention of Rescue Therapy [day] (95% CI) |                      |                      |                    |
| 25th  | XX.X (XX.X, XX.X)    | XX.X (XX.X, XX.X)    | XX.X (XX.X, XX.X)  |
| 50th (Median)   | XX.X (XX.X, XX.X)    | XX.X (XX.X, XX.X)    | XX.X (XX.X, XX.X)  |
| 75th  | XX.X (XX.X, XX.X)    | XX.X (XX.X, XX.X)    | XX.X (XX.X, XX.X)  |

p-value [1]

Note: NA = Not Applicable

Patient is considered having received rescue therapy if the patient 1) received rescue surgical procedure (penetrating keratoplasty or endothelial keratoplasty) during the study. 2) withdrawal with potential for surgical procedure. 3) withdrawal with potential for Rho kinase Inhibitor treatment.]

Patient's study discontinuation date is used as the rescue therapy date if the patient withdrawal with potential for surgical procedure or Rho kinase Inhibitor treatment.

Patients who completed follow-up or discontinued the study without receiving rescue therapy were [REDACTED]

[1] Two-sided p-value is from the log rank test.

Table 14.2.1.43

Central Corneal ECD (cells/mm^2) of Study Eye performed by Specular Microscopy by Visit (LOCF) via Wilcoxon Rank Sum Test (Full Analysis Set)

|                                   | K-321 QID
(N=XXX) | K-321 BID
(N=XXX) | Placebo
(N=XXX) |
|-----------------------------------|----------------------|----------------------|--------------------|
| Central Corneal ECD at Baseline   |                      |                      |                    |
| n                                 | XX                   | XX                   | XX                 |
| Mean (SD)                         | XX.X (XX.XX)         | XX.X (XX.XX)         | XX.X (XX.XX)       |
| Median                            | XX.X                 | XX.X                 | XX.X               |
| Q1, Q3                            | XX.X, XX.X           | XX.X, XX.X           | XX.X, XX.X         |
| Min, Max                          | XX, XX               | XX, XX               | XX, XX             |

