Note: BCVA = Best Corrected Visual Acuity, ETDRS= Early Treatment Diabetic Retinopathy Study

ECD = Endothelial Cell Density

Ass [REDACTED] be analysed and categorized as [REDACTED]

[figure not shown]
or [REDACTED] are not included.

Only [REDACTED] a observed are included.

Assessments after rescue keratoplasty are included using the collected values.

<DIRECTORY PATH>PROGRAM NAME Executed: DDMMYYYY hh:mm

Figure 14.2.1.42  
Time to Achieve Intervention of Rescue Therapy (Kaplan-Meier Plot)  
(Full Analysis Set)

Note: Time to Achieve Intervention of Rescue Therapy = Date of Achieving Intervention of Rescue Therapy - Day 1 + 1.

Patient is considered having received rescue therapy if the patient 1) received rescue surgical procedure (penetrating keratoplasty or endothelial keratoplasty) during the study. 2) withdrawal with potential for surgical procedure. 3) withdrawal with potential for Rho kinase Inhibitor treatment.]

Patient's study discontinuation date is used as the rescue therapy date if the patient withdrawal with potential for surgical procedure or Rho kinase Inhibitor treatment.

Patients who complete follow-up or discontinue the study without achieving the specified endpoint are

Source Data: T14.2.1.42

DIRECTORY PATH>PROGRAM NAME Executed: DDMMYYYY hh:mm

[figure not shown]
Programming note: Please show x-axis as Day 1 to Day 371. Please display y-axis label as 'Probability of Achieving Intervention of Rescue Keratoplasty (%)'.

Please display all treatment groups: K-321 QID, K-321 BID, Placebo

Figure 14.2.1.43

Central Corneal ECD (cells/mm^2) of Study Eye performed by Specular Microscopy (LOCF) (Time Series Plot) (Full Analysis Set)

Note: LOCF = last-observation-carried forward, ECD = Endothelial Cell Density  
Baseline is defined as the last measurement including unscheduled assessments prior to the administration of first dose of treatment.  
Central corneal ECD (both baseline and post-baseline) that are unable to be performed due to

assessment and analysis and central corneal ECD by [redacted] are [redacted].

[redacted]

T14 43

DIRECTORY PATH>PROGRAM NAME Executed: DDMMYYYY hh:mm

Programming note: Please show x-axis according to the analysis visit. Please display y-axis label as 'Mean(+/-SD) Central Corneal ECD (cells/mm^2) by Specular Microscopy'.  
Please display all treatment groups: K-321 QID, K-321 BID, Placebo  
Below the figure please include the N counts at each visit.  

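### The y-axis of Figure 14.2.1.42 names rescue keratoplasty, but the curve is a composite that also counts some withdrawals, and Table 14.2.1.42 does not show the components

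*SAP*

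**What the plan says.** Section 2 of the SAP addendum names the endpoint "Time to Intervention of Rescue Therapy" and compares each K-321 regimen with placebo by log-rank test. The definition is redacted there, but it is legible in the notes to Table 14.2.1.42 and Figure 14.2.1.42 in Appendix 1.

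The table note opens "Patient is considered having received rescue therapy if the patient 1) received rescue surgical procedure", meaning penetrating or endothelial keratoplasty. It then adds two kinds of withdrawal: one with a prospect of surgery, and "withdrawal with potential for Rho kinase Inhibitor treatment". On timing, the "study discontinuation date is used as the rescue therapy date if the patient withdrawal with potential for surgical procedure", and the same rule covers the Rho kinase inhibitor case.

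Table 14.2.1.42 has one event row, "Patients with Intervention of Rescue Therapy, n" (%), followed by quartiles of time to event and a p-value whose footnote reads "Two-sided p-value is from the log rank test". The figure takes this table as its source, and its title also says rescue therapy. Its programming note nevertheless prescribes the y-axis text "Probability of Achieving Intervention of Rescue Keratoplasty", with a percent sign.

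The addendum's Introduction says that these analyses were defined after the Week 12 unmasking. In protocol section 5.8.2 the rescue surgical procedures are penetrating or endothelial keratoplasty only.

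**The concern.** There are two separate faults.

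- **Label.** The axis describes a narrower event than the one plotted. In the protocol, rescue means keratoplasty, so a reader coming from it would naturally take the axis at its word and read the composite percentage as the percentage operated on.
- **Reporting.** The table counts patients who had no procedure as having received rescue therapy, and it pools them with those who had surgery. Whether a withdrawal carried a prospect of surgery or of a Rho kinase inhibitor is a judgement. With one total per arm and one p-value per comparison, the table cannot show how much of an arm difference is surgery performed and how much is withdrawal. Nothing in the documents shows bias or unmasked classification. That the analysis was defined after unmasking is still a good reason to show what drives the composite.

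**Working it through.** **Step 1: compare the texts.** All of these are legible, so redaction does not explain the mismatch.

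| Place (SAP addendum) | Event named |
|---|---|
| Section 2, endpoint name | Rescue therapy |
| Table 14.2.1.42, title, row and note | Rescue therapy, three components |
| Figure 14.2.1.42, title and note | Rescue therapy, the same three components |
| Figure 14.2.1.42, y-axis text | Rescue keratoplasty |

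Only the axis is out of line. The third component is not a keratoplasty, and the second does not need one to have been done.

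**Step 2: size of the axis error.** The plan gives no figure to reproduce. Protocol section 7.4 gives 20 patients per arm; the event counts below are assumed. With *k* keratoplasties, *w* counted withdrawals and no other early censoring, the composite curve ends at (k + w)/20. The keratoplasty-only curve ends at k/20 if all withdrawals come after the surgeries, and at k/(20 − w) if all come before.

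| k + w | Composite | Keratoplasty only | Gap per withdrawal (points) |
|---|---|---|---|
| 3 + 1 | 4/20 = 20.0% | 3/20 to 3/19 = 15.0–15.8% | 4.2–5.0 |
| 2 + 2 | 20.0% | 2/20 to 2/18 = 10.0–11.1% | 4.4–5.0 |
| 1 + 3 | 20.0% | 1/20 to 1/17 = 5.0–5.9% | 4.7–5.0 |
| 7 + 1 | 8/20 = 40.0% | 7/20 to 7/19 = 35.0–36.8% | 3.2–5.0 |

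For scale, protocol section 7.4 assumes about 5% of Week 12 values affected by withdrawal: 0.05 × 20 = 1 patient per arm, and the chance of at least one in an arm is 1 − 0.95^20 = 0.64. That rate covers all withdrawals. The number that would meet the composite definition by Week 52 is not given.

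**Step 3: effect on the log-rank result.** With one event at each distinct time, Z = (O − E)/√V, where E = Σ n_P/(n_P + n_A) and V = Σ n_P·n_A/(n_P + n_A)². O is the number of placebo events; n_P and n_A are the placebo and active patients at risk.

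Example: 3 placebo keratoplasties, 0 active, and 1 counted placebo withdrawal.

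- Composite (4 v 0): E = 20/40 + 19/39 + 18/38 + 17/37 = 1.920, V = 0.997, Z = 2.08, p = 0.037.
- Keratoplasty only, withdrawal censored after the surgeries: E = 20/40 + 19/39 + 18/38 = 1.461, V = 0.749, Z = 1.78, p = 0.075.
- Keratoplasty only, withdrawal censored before them: E = 19/39 + 18/38 + 17/37 = 1.420, V = 0.747, Z = 1.83, p = 0.068.

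The grid used 0 to 8 placebo keratoplasties against an equal or smaller active number, leaving out 0 v 0: 45 − 1 = 44 pairs. Each pair was run under three withdrawal patterns, with 1,000 random draws of distinct event days from days 14 to 359 and non-events censored at day 364. A pair counts as changed if the keratoplasty-only and composite p-values lie on different sides of 0.05 in more than half the draws.

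| Counted withdrawals (placebo, active) | Pairs changed, of 44 | Example: keratoplasty-only p to composite p |
|---|---|---|
| 1, 0 | 4 | 5 v 1: 0.059–0.090 to 0.034–0.046 |
| 0, 1 | 5 | 4 v 0: 0.037–0.042 to 0.143–0.171 |
| 1, 1 | 2 | 4 v 0: 0.032–0.042 to 0.071–0.090 |

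The total is 4 + 5 + 2 = 11 of 3 × 44 = 132 scenarios. The change goes in either direction. In the other 121 the verdict is unchanged in most draws.

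**Step 4: can the components be separated?** Yes. Protocol section 5.8 has all surgery during the study recorded in the eCRF, section 4.2.2 has withdrawal reasons recorded, and section 5.8.2 keeps patients who have rescue surgery on the visit schedule.

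**The case against.** The confirmed error is one text string. The figure's own title and note state the composite in full, so a reader is misled only by trusting the axis over both. A composite with a disclosed definition is legitimate, and counting withdrawals with a prospect of surgery as events avoids censoring that may be informative. No document requires component rows. Primary SAP v2.0 was not available, and its outputs or the data listings may already give keratoplasty counts. The p-value belongs to an additional analysis, openly labelled as defined after unmasking, with no error control and no decision rule. The scenarios are assumed, and any small-sample p-value moves when an event is added.

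Much of this stands as a limit on priority. Correcting the label changes no estimate, the composite should stay, and a keratoplasty-only analysis would have few events and its own censoring problem. It does not remove either point. Programming the figure as specified would put a wrong description of the plotted quantity into the report, and the note that corrects the axis gives no counts. Primary SAP v2.0 may make the extra outputs unnecessary, but the wrong string is in this addendum whatever that plan contains.

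**Conclusion.** The concern holds. The axis text contradicts the endpoint it plots, and Table 14.2.1.42 does not show the make-up of the composite. With 20 per arm and the counts assumed above, the label overstates keratoplasty by 3.2 to 5.0 percentage points per counted withdrawal, and by zero if no withdrawal is counted. Pooling matters to the log-rank verdict for a minority of borderline counts, 11 of the 132 scenarios. That fraction depends on the chosen grid and is not a probability for this trial. The finding on component counts is confirmed for this table only. The primary endpoint and its test are untouched, but the correction should be made before the outputs are produced.

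**What to change.** 1. Change the y-axis text of Figure 14.2.1.42 so that it says rescue therapy.
2. Add three rows to Table 14.2.1.42, giving the number of patients in each arm with each component.
3. Beside the composite, show a Kaplan-Meier and log-rank analysis of keratoplasty performed, as a sensitivity analysis that supplements the composite and does not replace it.

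Omit item 2 or 3 if primary SAP v2.0 already provides it. The cost is one text string, three table rows, and one extra table and figure from data already in the eCRF. The drawback of item 3 is few events and possibly informative censoring of patients who leave for surgery, which its footnote should state. No rule for offering rescue changes.

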**Figure 14.2.1.48**  
BCVA by ETDRS by Central ECD Value by Visit (Scatter Plot)  
(Full Analysis Set)

Note: BCVA = Best Corrected Visual Acuity, ETDRS= Early Treatment Diabetic Retinopathy Study  
ECD = Endothelial Cell Density  
Baseline is defined as the last [redacted] measurement including unscheduled assessments prior to the administration of first dose of [redacted] ment.

[figure not shown]
Source Data: Table 14.2.1.48

DIRECTORY PATH>PROGRAM NAME Executed: DDMMYYYY hh:mm

Programming note: Please show x-axis according to the subgroups '1 < Central ECD Value <= Mean', 'Central ECD Value > Mean' 'and [REDACTED]'. Please display y-axis label as 'BCVA by ETDRS Letter Score'. Please display 'All Post-Baseline Visits' in the first page, then start the second page with 'Baseline', 'Week X'... Each visit should be on a separate page.

In each page please display all treatment groups: Total, K-321 QID, K-321 BID, Placebo  
In each page please include number of subjects under each treatment arm and subgroups under the plot.  
Please display the spearman correlation and p-value under the figure for each treatment group and total.

Figure 14.2.1.49  
Correlation between BCVA by ETDRS and Central Corneal ECD (Include [REDACTED] (Pearson and Spearman)  
(Full Analysis Set)

Note: BCVA = Best Corrected Visual Acuity, ETDRS= Early Treatment Diabetic Retinopathy Study  
ECD = Endothelial Cell Density  
Central corneal ECD assessments that are unable to be performed due [REDACTED].  
Ass [REDACTED] be a [REDACTED] ed an [REDACTED] s [REDACTED].  
or [REDACTED] by [REDACTED] [REDACTED] [REDACTED] [REDACTED].  
Ass [REDACTED] are [REDACTED] [REDACTED] [REDACTED].  
Source Data: Table 14.2.1.49

<DIRECTORY PATH>PROGRAM NAME Executed: DDMMYYYY hh:mm

Programming note: Please display x-axis label as 'Central Corneal ECD (cells/mm^2)'. Please display y-axis label as 'BCVA by ETDRS Letter Score'.  
Please display the scatter lot for total and each treatment group in separate pages.

Please include the spearman and perason correlation values and the corresponding p-values under the figure for each treatment group and total.

Figure 14.2.1.50

Correlation between BCVA by ETDRS and Central Corneal ECD (Include [REDACTED] Data) (No Corneal Oedema)  
(Pearson and Spearman)  
(Full Analysis Set)

Repeat Figure 14.2.1.49 but only include the visits where there is No Corneal Oedema.

Note: BCVA = Best Corrected Visual Acuity, ETDRS= Early Treatment Diabetic Retinopathy Study

ECD = Endothelial Cell Density

Ass [REDACTED] be an [REDACTED] sed an [REDACTED] as [REDACTED]  
or [REDACTED] by [REDACTED] are [REDACTED].  
Onl [REDACTED] a ob [REDACTED].  
Assessments after rescue keratoplasty are [REDACTED].  
Source Data: Table 14.2.1.50

Programming note: Please display x-axis label as 'Central Corneal ECD (cells/mm^2)'. Please display y-axis label as 'BCVA by ETDRS Letter Score'.  
Please display the scatter lot for total and each treatment group in separate pages.

Please include the spearman and perason correlation values and the corresponding p-values under the figure for each treatment group and total.

**Figure 14.2.1.51**  
Correlation between BCVA by ETDRS and Central Corneal ECD (Exclude [REDACTED] Data) (Pearson and Spearman)  
(Full Analysis Set)

Repeat Figure 14.2.1.49 but only include the visits where there is no imputed data.

Note: BCVA = Best Corrected Visual Acuity, ETDRS= Early Treatment Diabetic Retinopathy Study  
ECD = Endothelial Cell Density  
Central corneal ECD assessments that are unable to [REDACTED] and a [REDACTED] es  
[REDACTED] be analysed and categorized as [REDACTED] or [REDACTED]  
[REDACTED] are not included.  
[REDACTED] rescue keratoplasty are [REDACTED].  
Source Data: Table 14.2.1.51

<DIRECTORY PATH>PROGRAM NAME Executed: DDMMYYYY hh:mm

Programming note: Please display x-axis label as 'Central Corneal ECD (cells/mm^2)'. Please display y-axis label as 'BCVA by ETDRS Letter Score'.  
Please display the scatter lot for total and each treatment group in separate pages.  
Please include the spearman and perason correlation values and the corresponding p-values under the figure for each treatment group and total.

Figure 14.2.1.52

Correlation between BCVA by ETDRS and Central Corneal ECD (Exclude [REDACTED] Data) (No Corneal Oedema)  
(Pearson and Spearman)  
(Full Analysis Set)

Repeat Figure 14.2.1.49 but only include the visits where there is no imputed data and the visits where there is No Corneal Oedema.

Note: BCVA = Best Corrected Visual Acuity, ETDRS= Early Treatment Diabetic Retinopathy Study

ECD = Endothelial Cell Density

Ass [REDACTED] be analysed and categorized as [REDACTED]

or [REDACTED] are not included.

Only [REDACTED] a obs

Assessments after rescue keratoplasty are [REDACTED]

Source Data: Table 14.2.1.52

<DIRECTORY PATH>PROGRAM NAME Executed: DDMMYYYY hh:mm

Programming note: Please display x-axis label as 'Central Corneal ECD (cells/mm^2)'. Please display y-axis label as 'BCVA by ETDRS Letter Score'.

Please display the scatter lot for total and each treatment group in separate pages.

Please include the spearman and perason correlation values and the corresponding p-values under the figure for each treatment group and total.
